146 3.2 Secondary Endpoints

147 The changes from baseline for 18 weeks of liraglutide + metformin compared with glimepiride +
148 metformin treatment will improve or affect;

- 149 • Global LV function (echocardiography) expressed as ejection fraction (EF)
- 150 • Exercise ECG, including working capacity
- 151 • 24-hour blood pressure
- 152 • Energy delivering from the carotid artery
- 153 • N-terminal pro b-type natriuretic peptide (NT-proBNP) levels in serum over time and
- 154 symptoms of dyspnea or fatigue as assessed by patient and clinician using established
- 155 scoring systems.
- 156 • Gene expression (Affymetrix)
- 157 • Plasma markers of inflammation *i.e.* hsCRP, IL-6, TNF- α and PAI-1
- 158 • Plasma markers of endothelial activation *i.e.* E-selectin, VCAM-1, ICAM-1 and plasma
- 159 levels of nitrate/nitrite
- 160 • Lipids
- 161 • HbA_{1c}
- 162 • Body weight
- 163 • Adverse events in terms of hypoglycaemia
- 164 • Quality of life (SF 36)
- 165 • Blood test (venipuncture)

166 4 Design

167 4.1 Outline

168 The present trial is a two centre, open, assessor-blinded and active-controlled, parallel-group
169 trial, in combination with metformin. The trial will compare the treatment with liraglutide 1.8 mg
170 (s.c) QD + metformin up to 1 g BID, with that of glimepiride 4 mg QD (comparator) +
171 metformin up to 1 g BID, on LV function in subjects with type 2 diabetes.

172 Patients are asked to participate in the study and after informed and written consent has been
173 obtained, subjects will be screened based on the inclusion and exclusion criteria. If needed,
174 subjects will have metformin up-titrated to a maximal daily dose of 2g, or the highest tolerated
175 dose in the run-in period. Total trial duration for the individual subject will be 18 ± 4 weeks. A
176 population of 80 type 2 diabetic subjects will be investigated (Figure 1).

[figure not shown]
Protocol No: EudraCT nr 2010022695-31

Date: 20110204

Version: 7.5

10(30)

Fig 1.

177

178 4.2 Assessments and Procedures

179 The subjects will attend a screening visit (Visit 1) in order to assess their eligibility. If found
 180 eligible, the subjects will return at Visit 2 within approximately 4 weeks, after Visit 1, with an
 181 up-titration with metformin 1 g BID or the maximal tolerated dosage of metformin (Run-in
 182 period).

183 At Visit 2 patients will be tested for;

- 184 • Heart function at rest and during an exercise ECG Stress Test with tissue Doppler

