392 saved and transmitted to a work station (EchoPAC-PC version 60; GE Medical systems) for off-
393 line analysis.

394 **7.1.5 Exercise ECG Stress Test and Tissue Doppler Echocardiography**

395 A bicycle exercise stress test, following a standard protocol, will be performed using a Case 5
396 system (GE Medical Systems, WI, USA) immediately after the work. A stepwise increase of 20
397 W in working-load capacity will be changed every other minute. Subjects' will be asked to finish
398 the work accordingly to the Borg scale 14-15. The electrocardiogram (ECG) will be monitored
399 with a 12 lead ECG devices.

400 **7.1.6 Adverse events**

401 Adverse Events will be recorded at each visit in accordance with the procedures described in
402 section 8. Any clinically significant worsening since baseline of a previous finding must be
403 reported as an AE.

404 **7.1.7 Hypoglycaemic episodes**

405 Blood glucose should always be measured when there is a suspicion of a hypoglycaemic episode.
406 All plasma glucose values ≤ 3.9 mmol/l when hypoglycaemic symptoms have occurred will be
407 recorded by the subjects in the diaries and transcribed into the CRF.

408 A hypoglycaemic episode will be defined as treatment emergent if the onset of the episode is on
409 or after first day of trial product. The recording should include:

- 410 • Date
- 411 • Time of hypoglycaemic episode
- 412 • Time of last liraglutide/glimepiride dose prior to episode
- 413 • Amount of last liraglutide/glimepiride dose prior to episode
- 414 • Time of last main meal prior to episode
- 415 • Whether the episode was symptomatic
- 416 • Whether the episode was in relation to exercise
- 417 • Whether hypoglycaemic re-occurred in the 24-hrs after initial recovery
- 418 • If yes, approximately number of hours since the first hypoglycaemic episode
- 419 • Whether the subject was able to treat him/herself, whether he/she recovered with oral
420 administration of carbohydrates
- 421 • The plasma glucose level before treating the episode

422 Hypoglycaemic episodes will be defined as nocturnal if the time of onset is between 00:01
423 (included) and 05:59 am (included).

424 Documentation of hypoglycaemia by data from the Glucometer being downloaded at the next
425 visit using Diasend[®].

426 A hypoglycaemic episode form must be filled in for all hypoglycaemic episodes. If the
427 hypoglycaemic episodes fulfil the criteria of a serious AE, a hypoglycaemic episode Form, an

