428 AE form and a Safety Information Form must be filled in.

429 ADA definitions and classification of hypoglycaemia will be applicable:

430 **Severe hypoglycaemia:** an episode requiring assistance of another person to actively administer
431 carbohydrate, glucagons, or other resuscitative actions.

432 **Documented hypoglycaemia:** an episode during which typical symptoms of hypoglycaemia are
433 accompanied by measured plasma glucose concentration ≤ 3.9 mmol/l.

434 **Asymptomatic hypoglycaemia:** an episode not accompanied by typical symptoms
435 hypoglycaemia, but with a measured plasma glucose concentration ≤ 3.9 mmol/l.

436 **7.1.8 Physical examination**

437 Physical examination will include:

- 438 • Head, ears, nose, throat, neck
- 439 • Lungs
- 440 • Cardiovascular system
- 441 • Gastrointestinal system
- 442 • Vital signs

443 In the case of an abnormal clinical significant finding, the Investigator must comment in the
444 subject notes.

445 Any clinically significant worsening from baseline must be reported as an AE.

446 **7.2 Laboratory Efficacy Assessments**

447 For laboratory analysis of efficacy parameters a total of approximately 100 ml blood will be
448 drawn during the 18 weeks of the trial. The laboratory analyses will be performed by a central
449 laboratory unless otherwise specified. Description of assays methods, laboratory supplies and
450 procedures for obtaining samples, handling and storage of samples and information on who will
451 perform the assessments, will be described in a trial specific laboratory manual provided by a
452 central laboratory.

453 Laboratory samples can be drawn on a day other than the day the visit is performed as long as it
454 is within the visit window stated in the flowchart. For some of the samples drawn during the trial
455 it is required for the sensitivity of the analysis that the subject is fasting.

456 Samples will be coded such that the subject identity will remain anonymous.

457 Blood samples will be drawn for the efficacy assessments to determine levels of following:

- 458 • HbA_{1c}
- 459
- 460 • Fasting plasma glucose
- 461
- 462 • Lipids – Subject must be fasting
 - 463 ○ Total Cholesterol
 - 464 ○ HDL Cholesterol
 - 465 ○ LDL Cholesterol
 - 466 ○ Triglycerides
- 467 • Plasma markers of inflammation
 - 468 ○ hsCRP
 - 469 ○ IL-6
 - 470 ○ TNF- α
 - 471 ○ PAI-1
- 472

Protocol No: *EudraCT nr 2010022695-31*

Date: *20110204*

Version: *7.5*

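### Section 7.1.7 sends low glucose values to the diary and CRF only when symptoms occurred, yet defines an asymptomatic class and asks for symptom status, so that class risks being under-counted or misclassified

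*Protocol*

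**What the plan says.** All of the following is in the protocol.

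- **Recording rule (7.1.7).** "All plasma glucose values ≤ 3.9 mmol/l when hypoglycaemic symptoms have occurred will be" "recorded by the subjects in the diaries and transcribed into the CRF". Entry needs both a low value and symptoms.
- **When to test outside the schedule (7.1.7).** "Blood glucose should always be measured when there is a suspicion of a hypoglycaemic episode".
- **Fields to record (7.1.7).** The list includes "Whether the episode was symptomatic", along with the time and amount of the last trial drug dose, the time of the last main meal and any relation to exercise.
- **Classification (7.1.7).** "ADA definitions and classification of hypoglycaemia will be applicable". The third class is "an episode not accompanied by typical symptoms" of "hypoglycaemia, but with a measured plasma glucose concentration ≤ 3.9 mmol/l".
- **Other routes into the data.** Section 7.1.7 also has the glucose meter downloaded at the next visit and makes an episode form compulsory for every episode. Neither provision carries a symptom condition. Section 4.2 schedules 7-point profiles around Visits 3 to 6, with electronic transfer of the values.
- **Endpoint (3.2).** "Adverse events in terms of hypoglycaemia" is a secondary endpoint. It is not split by class.

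**The concern.** The diary rule leaves out exactly the values that make up the third class. The diary is also the only record described in 7.1.7 that the subject writes at the time. The meter holds glucose values; nothing in the protocol says that it holds symptoms, dose, meal or exercise.

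A low value that appears in the download without a diary entry then has two possible explanations: the subject had no symptoms, or had symptoms and did not write them down. The first is an asymptomatic episode and the second a documented one. The two cannot be told apart unless symptom status was noted at the time.

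This bears on a listed secondary endpoint in an open trial. Subjects know their drug, and under the present rule their judgement of whether they had symptoms decides whether a low value is written down at all. A statistical analysis plan can choose which classes to count, but it cannot recover symptom status that was never collected.

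**Working it through.** The protocol states no figure on this point, so the check sets the provisions side by side and asks what happens to a measured value of 3.9 mmol/l or lower without symptoms.

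1. **Diary and CRF rule:** not entered, because the symptom condition is not met.
2. **Asymptomatic class:** the value meets the definition, so it is an episode under the classification that the protocol adopts.
3. **Symptom field:** it is informative only if episodes without symptoms are recorded. For episodes that enter through the diary rule alone it could take only one value.
4. **Episode form:** required, since the value is an episode by step 2. Steps 1 and 4 therefore give opposite instructions on whether the subject's own account is written down.
5. **Meter download:** the value is present, but the text does not say that finding it there starts an episode form, or which source defines the count.

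**Delay before the value is seen.** The Schedule of Investigational Events places Visit 2 at week 0, Visit 3 at week 2, Visit 4 at week 10 and Visit 5 at week 18. Section 4.2 makes Visits 3 and 4 telephone contacts. The text does not say whether a download takes place at a telephone contact.

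- If it needs attendance, the longest gap is 18 − 0 = 18 weeks.
- If transfer is possible at the telephone contacts, the longest gap up to Visit 5 is 10 − 2 = 18 − 10 = 8 weeks.

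Under either reading, the details of a single reading could be asked for weeks after it was taken.

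**Scheduled readings that could show such a value.** The wording in 4.2 allows two readings of the profile schedule.

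- Three days at each of the four time points: 7 × 3 × 4 = 84 readings per subject.
- Three days before Visit 3 and one day at each of Visits 4, 5 and 6: 7 × 3 + 7 × 1 × 3 = 21 + 21 = 42 readings per subject.

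These counts show that asymptomatic values can be detected. They measure testing, not under-counting. Because unscheduled tests are prompted by suspicion, asymptomatic values would be found mainly in these profiles.

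**Size.** An under-count would need the rate of asymptomatic low values in each arm and the share of them that never leads to a form. The protocol gives neither, so no figure follows.

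**The case against.** The strongest reply is that the diary is not the only route. The compulsory episode form has no symptom condition, and the asymptomatic class is defined as an episode, so a recognised asymptomatic episode requires a form. The profiles are measured whether or not there are symptoms. Both telephone visits include self-reported glucose values, and adverse events are asked about at every contact. The symptom field need not be tied to the diary sentence and may simply show that asymptomatic episodes were meant to be captured. The endpoint is not split by class, and no separate asymptomatic count is fixed.

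Most of this stands. A reader might infer that the asymptomatic class will be empty in the CRF, or that it is certainly under-counted. The documents support neither, because these other routes exist. A reader might also infer a bias between arms from the open design. The documents give no basis for its size or direction, and symptom reports by subjects who know their drug would remain open to this influence under any recording rule.

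What the reply does not remove is the conflict in the text. The form depends on someone recognising the episode, and nothing says that a download value counts as recognition. Questions at a telephone contact may come up to 8 weeks after the reading. If the field shows that asymptomatic episodes were intended, the diary sentence is the one that is worded wrongly.

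**Conclusion.** The concern holds as an internal contradiction in 7.1.7 with a risk of under-counting or misclassifying asymptomatic hypoglycaemia. It does not hold as a demonstrated loss of data.

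The conclusion rests on two readings of silence in the protocol: that the meter data carry glucose values without symptoms or circumstances, and that a low value found only in the download does not automatically start an episode form. If the site procedures or the meter settings provide otherwise, the risk shrinks, although the wording still needs to be reconciled. The size cannot be computed from the documents. The point is minor: it touches one class within one secondary endpoint and leaves the primary comparison alone. It is worth correcting because it is cheap before data collection and cannot be repaired at analysis.

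**What to change.** In 7.1.7, delete the clause that makes diary entry conditional on symptoms, so that every measured plasma glucose value of 3.9 mmol/l or lower goes into the diary and the CRF, with symptom status noted by the subject at the time. Add one sentence stating that low values found in the meter download are reconciled with the diary and trigger the episode form.

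The cost is a change of wording in 7.1.7 and in the diary, and a few more diary lines per subject. The change will not make symptom reporting independent of knowledge of treatment. It will stop symptom reporting from deciding whether a low value is written down.

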- 185 echocardiography
- 186 • 24-hour blood pressure
- 187 • Antropometric assessment
- 188 • Symptoms of dyspnea or fatigue (scoring system, classified as NYHA).
- 189 • Quality of life (SF 36)
- 190 • Blood test (venipuncture)
- 191 • U-HCG (in fertilized women)

192 Subsequently thereafter, subjects will during visit 2 be randomized to receive either liraglutide
 193 1.8 mg s.c. (initial dose of 0.6 mg with an up-titration of 0.6 mg every week, final dose 1.8 mg
 194 QD) or glimepiride 4 mg p.o (initial dose of 2 mg, with an up-titration of 1 mg every week, final
 195 dose 4 mg QD).

196 At Visit 2, subjects will be supplied with a glucose meter (Abbot Contour) and instruction on use
 197 of the device including regular calibration according to the manufacturer's instruction. Subject
 198 will also be provided with written instruction. The glucose meter use test strips calibrated to

Protocol No: EudraCT nr 2010022695-31

Date: 20110204

Version: 7.5

199 plasma values. Therefore all glucose measurements performed with drawn capillary blood are
200 automatically calibrated to plasma equivalent glucose values, which will be shown on the display
201 and are the values to be used.

202 Subjects will be instructed on how to record the results of the self measured plasma glucose
203 (SMPG) values in the meter. Subjects will then ask to monitor a 7 point profile glucose curve
204 consecutively in three days before visit 3, at visit 4 and at the end of treatment (visit 5) and at the
205 end of the trial (visit 6). SMBG values will be transferred via a computerized system (Diasend[®]).

206 Visit 3. Telephone visit. Self-reporting glucose measurements.

207 Visit 4. Telephone visit. Self-reporting glucose measurements.

208 At week 18 (Visit 5), subjects will be re-tested for:

- 209 • Heart function at rest and during an exercise ECG Stress Test with tissue Doppler
- 210 echocardiography
- 211 • 24-hour blood pressure
- 212 • Antropometric assessment
- 213 • Symptoms of dyspnea or fatigue (scoring system, classified as NYHA).
- 214 • Quality of life (SF 36)
- 215 • Blood test (venipuncture)
- 216 • U-HCG (in fertilized women)

217 The physician will decide what treatment patients will be continued on Visit 6. Follow up and re-
218 evaluate the anti-diabetic treatment. At all contacts Investigators will ask subject for signs or
219 symptoms of an AE.

220 **4.3 Schedule of Investigational Events**

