221 Procedures for the scheduled visits and phone contacts are described in the section above and in
222 the flowchart (Schedule of Investigational Events, Appendix 17. 1). Each subject will be
223 followed approximately 18 ± 4 weeks after randomisation.

224 **5 Selection and Withdrawal of Subjects**

225 **5.1 Inclusion Criteria**

- 226 1 Type 2 diabetes.
- 227 2 Heart Failure, visualized with echocardiography, one of the following (2.1, 2.2 or 2.3).
 - 228 2.1 Ejection Fraction $\leq 50\%$.
 - 229 2.2 Decreased systolic velocity (four chamber view) where two, out of four segments (Septum,
230 Lateral, Inferior and Anterior Wall) has a relative decrease in velocity of 20% compared to
231 a normal population.
 - 232 2.3 Evidence of diastolic dysfunction as shown by abnormal left ventricular relaxation, filling,
233 diastolic distensibility or stiffness. An E/E' ratio (ratio of early diastolic velocities of mitral
234 inflow derived Doppler imaging and myocardial movement derived by tissue Doppler

- 235 imaging) >15 is considered diagnostic of diastolic dysfunction and an E/E' ratio < 8 as
236 diagnostic of the absence of diastolic heart failure. An increased left atrial size (>49 ml/
237 m^2) and an increased left ventricular mass (>122 g/ m^2 in women and >149 g/ m^2 in men)
238 are considered sufficient evidence of diastolic dysfunction when the E/E' ratio is
239 inconclusive.
- 240 3 HbA_{1c} (accordingly to IFCC) 60 mmol/mol – 95 mmol/mol.
241 4 If antihypertensive treatment, the medication has to be stable, no change, for the last 1
242 month.
243 5 Male and female subjects, 18-70 years of age.
244 6 Signed informed consent form.

245 5.2 Exclusion Criteria

- 246 1. Type 1 diabetes (autoantibody positive).
247 2. Any history of receiving GLP-1 analogues or dipeptidyl peptidase inhibitors (DPP-IV
248 inhibitor) or glimeperid.
249 3. Previous treatment with glitazones within 6 months.
250 4. Previous treatment with other sulphonylurea within 3 months.
251 5. Previous treatment with insulin (any regimen) within 1 month.
252 6. Known severe heart failure, classified as NYHA 3-4.
253 7. Significant ischemic heart disease (defined as angina-limited exercise or unstable angina);
254 documented acute myocardial infarction (MI) within the previous 8 weeks.
255 8. Active myocarditis; malfunctioning artificial heart valve.
256 9. Atria fibrillation or flutter
257 10. History of ventricular tachycardia within 3 months before study entry; second- or third-

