258 degree atrioventricular block.
259 11. Implanted pacemaker.
260 12. Supine systolic blood pressure <85 mm Hg or >200 mm Hg.
261 13. Primary renal impairment (creatinine clearance < 30 ml/min), or creatinine clearance $<$
262 60 ml/min if treated with metformin.
263 14. Uncorrected hypokalemia or hyperkalemia (potassium <3.5 mmol/l or >5.5 mmol/l).
264 15. Significant anemia (Hb < 90 g/l)
265 16. Treatment with another investigational agent within 30 days before study entry, judged
266 by the investigator.
267 17. Severe gastrointestinal disease, including gastroparesis. As judged by the investigator.
268 18. Body mass index (BMI) > 40 kg/ m^2 .
269 19. Malignant neoplasm requiring chemotherapy, surgery, radiation or palliative therapy in
270 the previous 5 years. Patients with intraepithelial squamous cell carcinoma of the skin
271 treated with topical 5FU and subjects with basal cell skin cancer are allowed to enter the
272 trial.
273 20. Females of child bearing potential who are pregnant, breast-feeding or intend to become
274 pregnant or are not using adequate contraceptive methods (adequate contraceptive
275 measures as required by local law or practice).
276 21. Current drug and alcohol abuse.
277 22. History of acute or chronic pancreatitis
278 23. Subjects considered by the investigator to be unsuitable for the study.

279 **5.3 Criteria for Withdrawal**

280 The subjects may withdraw at will at any time. The subjects may be withdrawn from the trial at
281 the discretion of the Investigator due to safety concerns or if judged non-compliant with trial
282 procedures. Subjects randomised in error must be withdrawn from the trial

283 A subject must be withdrawn if the following applies:

- 284 1. Pregnancy or intention of becoming pregnant
- 285 2. Participation in other trials throughout the trial
- 286 3. Serious heart failure or a cardiovascular event

287 **5.4 Subject Log**

288 All subjects in the screening process will be documented in a medical chart accordingly to their
289 inclusion criteria or exclusion criteria.

290 **6 Treatment**

291 All subjects have been instructed to up-titrate metformin to 1 g BID, or maximal tolerated dose
292 of metformin, before randomisation (run-in period). At randomisation (Visit 2) subjects will be
293 randomised into one of the two treatment groups; liraglutide 1.8 mg (s.c) QD (initial dose of 0.6
294 mg with an up-titration of 0.6 mg every week, final dose 1.8 mg) or glimepiride 4 mg (p.o) QD

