295 (initial dose of 2 mg, with an up-titration of 1 mg every week, final dose 4 mg), both in
296 combination with metformin 1 g BID.

297 Subjects will be instructed to take metformin meanwhile the breakfast and the dinner meal.

298 Subjects will be instructed to take glimepiride before the breakfast meal and liraglutide at the
299 same time point every day.

300 **6.1 Description of Investigational Medicinal Products**

301 Liraglutide will be available as a solution for injection at a concentration of 6.0 mg/ml, supplied
302 in a 3 mL pre-filled disposable pen.

303 Glimepiride will be available as tablet for oral administration, each tablet containing 1 mg, 2 mg
304 or 4 mg of glimepiride.

305 **6.2 Packaging, Labelling, Storage and Handling of Investigational Medicinal Products**

306 The trial products will be packed and labelled by an external clinical supply contractor, which
307 can be done since both trial products are commercially available. Labelling will be in accordance
308 with Annex 13, local law and trial requirements.

309 Each investigator site will be supplied with sufficient trial products for the trial.

310 Trial product will be packed in dispensing units and will be distributed to the sites according to
311 enrolment and randomisation.

312 The trial products will be dispensed to each subject at Visit 2, as required according to treatment
313 group. The randomisation procedure will allocate trial product Dispensing Unit Number (DUN)
314 to the subject at the dispensing visit. The correct DUN must be dispensed to the subject at the
315 dispensing visit.

316 Instruction to the subject on how to use the trial liraglutide pre-filled disposable pen should be
317 provide by the Investigator at Visit 2.

318 The trial products should be stored in accordance with the storage conditions as stated in the
319 Summary of Product Characteristics for each product, see Appendices 17.2 and 17.3.

320 The Investigator must ensure availability of proper storage conditions, and record and evaluate
321 the temperature (at least every working day). Storage facilities should be checked frequently. A
322 log to document the temperature must be kept.

323 Storage and in-use conditions:

324 Liraglutide

325 Not in use: The liraglutide pre-filled pen must be stored in a refrigerator at a temperature between
326 +2°C and + 8°C. Keep away from the cooling element. Do not freeze and do not use if it has
327 been frozen.

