- 522 potential, at visit 1 and visit 5. For those of childbearing potentials the required use of
- 523 contraceptives will be discussed.
- 524
- 525 ● Urine samples
- 526 ○ Albumin/creatinine ratio by urine spot

527 8 Proceedings for Adverse Events

528 8.1 Definition of Adverse Events

529 8.1.1 Definition of Adverse Events

530 An Adverse Event (AE) is any untoward medical occurrence in a subject administered
531 Investigational Medicinal Products (IMP) and which does not necessarily have a causal
532 relationship with this product. An AE can be any unfavourable and unintended sign, abnormal
533 laboratory finding, symptom or disease temporally associated with the use of IMP, whether or
534 not related to the product.

535 8.1.2 Definition of Adverse Reactions

536 Each AE is to be classified by the investigator as related or not related to the IMP. An Adverse
537 Reaction (AR) is a noxious and unintended medical response to a medical product related to any
538 dose. For an AE to be an AR the suspected association between the product and the unwanted
539 medical condition should be at least a reasonable possibility.

540 8.1.3 Definition of Serious Adverse Events

541 Each AE is to be classified by the investigator as serious or non-serious. Seriousness is not
542 defined by a medical term; it is a result or an outcome. An AE is defined as a Serious Adverse
543 Event (SAE) if it:

- 544 ● results in death
- 545 ● is life-threatening
- 546 ● requires inpatient hospitalisation or prolongation of existing hospitalisation
- 547 ● results in persistent or significant disability/incapacity
- 548 ● results in a congenital anomaly/birth defect
- 549 ● Important medical events that may not result in death, be life-threatening, or require
- 550 hospitalisation may be considered an SAR when, based upon appropriate medical
- 551 judgement, they may jeopardise the patient and may require medical or surgical
- 552 intervention to prevent one of the outcomes listed in this definition

553 Medical and scientific judgement should be exercised in deciding whether expedited reporting is
554 appropriate in other situations, such as important medical events that may not be immediately
555 life-threatening or result in death or hospitalisation but may jeopardise the patient or may require
556 intervention to prevent one of the other outcomes listed in the definition above. These should also

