588 available. The original SAE form must be filed with the CRF. The sponsor shall report all cases
589 of death to the MPA within 7 days, and if necessary complete the report to the MPA within 8
590 days and all cases of death to the Independent Ethics Committee (IEC).

591 **8.4.3 Reporting of Suspected Unexpected Serious Adverse reactions**

592 The sponsor must report all SUSARs that resulted in death or was life threatening to the authority
593 through the EudraVigilance database and to the IEC within 7 days, and if necessary complete the
594 report within the following 8 days. Other SUSAR should be reported within 15 days. In addition
595 will the sponsor report all SUSAR to all Principal Investigators involved in trials with the IMP.

596 **8.5 Follow-up of Adverse Events**

597 *Follow-up information (corrections, new or additional information) should be reported within*
598 *the timeline of obtaining knowledge of the information for SAEs, and if previously non-serious*
599 *AEs become SAEs to the Sponsor. The Investigator must ensure that the worst case severity and*
600 *seriousness is kept consistent.*

601 During and following a subject's participation in a clinical trial, the Investigator/institution
602 should ensure that adequate medical care is provided to the subjects for any AE(s), including
603 clinically significant laboratory values related to the trial. The investigator should inform the
604 subject when medical care is needed for AE(s) of which the Investigator becomes aware.

605 The follow up information should only include new (updated and/or additional) information that
606 reflects the situation at the time of the Investigator's signature.

607 **8.6 Pregnancy**

608 Subjects must be instructed to notify the Investigator immediately if they or their partner become
609 pregnant during the trial.

610 The Investigator must report any pregnancy reported during the trial except for pregnancies
611 occurring in the screening period. Trial subjects will give consent on enrolment that the
612 Investigator will document any pregnancy during the trial, and that she will be asked to provide
613 information about her pregnancy, delivery and the health of her infant until age one month. If the
614 pregnancy results in an abnormal outcome, such as congenital anomalies, foetal death,
615 spontaneous abortion, or SAEs in the neonate then this should be regarded as an SAE with the
616 same reporting requirements and timelines as for SAE.

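### The protocol places the pre-treatment pregnancy test at Visit 2 in section 4.2 but at Visit 1 in section 7.3 and the schedule, so drug could be dispensed on a result 1 to 4 weeks old

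*Protocol*

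**What the plan says.** Three places in the protocol time the pregnancy test.

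- **Section 4.2** includes "U-HCG (in fertilized women" in the list of Visit 2 tests and again in the Visit 5 list. It names no Visit 1 pregnancy test. Straight after the Visit 2 list it continues: "Subsequently thereafter, subjects will during visit 2 be randomized to receive either liraglutide". On this text the test comes before allocation, at the same visit.
- **Section 7.3** calls for a urine U-HCG in females of childbearing "potential, at visit 1 and visit 5. For those of childbearing potentials the required use of" contraception is to be discussed. It names no Visit 2 test.
- **The Schedule of Investigational Events** in the appendix marks the pregnancy test at Visit 1 (week -4 to -1) and Visit 5 (week 18), with no mark at Visit 2 (week 0).

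Dispensing is fixed at Visit 2 in section 6.2: "The trial products will be dispensed to each subject at Visit 2, as required according to treatment" group. The schedule agrees.

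Section 4.3 links the lists: "Procedures for the scheduled visits and phone contacts are described in the section above and in" the flowchart. It does not say which prevails where they differ.

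**The concern.** All three places agree on the test at the end of treatment. They differ only on the test before treatment, which is the one that protects a fetus from exposure to trial drug. Pregnancy is an exclusion (5.2, criterion 20: "Females of child bearing potential who are pregnant, breast-feeding or intend to become" pregnant) and a ground for mandatory withdrawal (5.3: "Pregnancy or intention of becoming pregnant"), so the protocol clearly means that no pregnant woman should start treatment. A test at screening followed by a run-in of some weeks leaves an interval in which a conception would go undetected when the first dose is given. Whether that interval is covered depends on which page a site works from. With two centres, practice could differ between them.

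**Working it through.** No sample size, power or error rate is involved, and the protocol gives no figure here to reproduce. The check compares the three lists and subtracts schedule weeks.

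**Inputs.** Visit 1 is week -4 to -1, Visit 2 is week 0 and Visit 5 is week 18 (schedule). Section 4.2 has the subject return for Visit 2 within about 4 weeks of Visit 1, which agrees.

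| Source | Visit 1 | Visit 2 | Visit 5 |
|---|---|---|---|
| Section 4.2 | no | yes | yes |
| Section 7.3 | yes | no | yes |
| Schedule | yes | no | yes |

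One source of three has a Visit 2 test, and two do not.

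**Age of the latest result at dispensing** = week of dispensing minus week of test.

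- Under 7.3 or the schedule: 0 - (-1) = 1 week at least, and 0 - (-4) = 4 weeks at most.
- Under 4.2: 0 - 0 = 0 weeks.

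**Time from first dispensing to the next scheduled test** = 18 - 0 = 18 weeks on any reading. Visits 3 and 4 are telephone contacts with no pregnancy test. Under 7.3 or the schedule the gap between consecutive tests is 18 - (-1) = 19 to 18 - (-4) = 22 weeks.

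**Does another rule close the gap?** Section 7.3 lets samples be drawn on a different day from the visit, but only inside the window given in the flowchart. A Visit 1 sample therefore still falls in week -4 to -1 and cannot be moved to week 0 under that rule.

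**Combined reading.** Taking all the lists together gives tests at Visits 1, 2 and 5, which is 3 tests. Each source alone gives 2, so the combined reading adds 3 - 2 = 1 test per woman.

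**The case against.** The strongest reply is that the lists do not exclude one another. Section 4.3 says that procedures are described both in the preceding section and in the flowchart, and the natural sense is that both apply. A site reading it that way tests at Visits 1, 2 and 5. One that omits the Visit 2 test departs from 4.2, and the monitor checks adherence (10.1). A positive Visit 2 test would also stop randomisation without any further rule: 4.2 puts the tests first, and criterion 20 excludes the woman. This stands as a fair reading, and it is why the problem is only a possible one. It does not remove the inconsistency, because 7.3 and the schedule each give a complete-looking list without the Visit 2 test, and a schedule is what sites commonly work from.

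Other safeguards also reduce the risk. Adequate contraception is required, pregnancy leads to withdrawal, and subjects must report a pregnancy at once (8.6). These lower the chance of pregnancy or act once it is known. They do not detect an unrecognised pregnancy before the first dose.

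Three stronger readings are tempting, but the protocol does not support them.

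- A reader might infer that women could be dosed untested. Every version has a test before the first dose; only its timing differs.
- A reader might infer from the schedule's single eligibility mark at Visit 1 that a Visit 2 result would be ignored. The same schedule first shows echocardiography and blood chemistry at Visit 2, although several eligibility criteria depend on such data. That mark cannot be taken to mean that eligibility closes at Visit 1.
- A reader might infer from 8.6 ("The Investigator must report any pregnancy reported during the trial except for pregnancies" in the screening period) that such a pregnancy would be lost. That exemption concerns reporting, not detection. The same section has the investigator document any pregnancy during the trial and treats abnormal outcomes as serious adverse events.

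The wording of the group in 4.2 is an evident slip for fertile women and carries no weight.

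**Conclusion.** The point holds as a minor internal inconsistency with a safety aspect. Section 4.2 gives a same-visit test before randomisation. Section 7.3 and the schedule do not, and a site following either would dispense on a result 1 to 4 weeks old, with nothing further scheduled until week 18.

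This rests on two assumptions: that the schedule's visit weeks are kept, and that at least one site works from 7.3 or the schedule without adding the 4.2 test. The practical effect cannot be sized, because the protocol does not say how many of the 80 subjects, aged 18 to 70, would be women of childbearing potential. The primary endpoint and the sample size are unaffected.

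**What to change.** Put the same statement in 4.2, 7.3 and the Schedule of Investigational Events: U-HCG in females of childbearing potential at Visit 1, at Visit 2 with a negative result required before randomisation and dispensing, and at Visit 5. Use that description of the group in 4.2 as well.

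The cost is text corrections in three places and at most one additional urine test per woman concerned. Section 4.2 already lists the Visit 2 test, so a site that combines the lists would do no more than it does now.
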